6.7 Weeks 2, 4, 6, and 8 (+/- 2 days)

The following assessments and procedures will be performed unless otherwise stipulated:

- Review and record concomitant medications.
- Physical examination.
- Vital signs.
- Assessment of AEs.
- ERT administration log.
- Pregnancy test (females of childbearing potential only; at Weeks 4 and 8 only).
- Clinical laboratory tests.

- Liver panel (twice weekly; may be conducted at home if subject is remote).
- GAG testing in urine.
- IDS / GAG testing in blood.
- Circulating AFP level (at Weeks 4 and 8 only).
- Vector genome PCR in plasma, saliva, urine, stool, and semen (males only) (at Weeks 2, 4, and 8 only).
- Immunogenicity assays (at Week 4 only).
- Prednisone or equivalent corticosteroid administration.

6.8 Weeks 12, 16, 20, 24, 28, 32, 36, 40, 44, 48, and 52 (+/-1 week)

The following assessments and procedures will be performed unless otherwise stipulated:

- Review and record concomitant medications.
- Physical examination (at Weeks 12, 16, 20, 24, 36, and 48 only).
- Vital signs (at Weeks 12, 16, 20, 24, 36, and 48 only).
- Assessment of AEs.
- ERT administration log.
- JROM (at Weeks 24 and 48 only).
- Neurologic cranial nerve exam and muscle strength testing of the upper extremities (at Weeks 24 and 48 only).
- 12-lead ECG (at Weeks 24 and 48 only).
- ECHO (at Week 48 only).
- Pregnancy test (females of childbearing potential only; at Weeks 12, 16, 20, 24, 36, and 48 only).
- Clinical laboratory tests (at Weeks 12, 16, 20, 24, 36, and 48 only).
- Liver panel (twice weekly until Week 20; then at Weeks 24, 28, 32, 36, 40, 44, 48, and 52; may be conducted at home if subject is remote until Week 20 and at Weeks 28, 32, 40, 44, and 52).
- GAG testing in urine.
- IDS / GAG testing in blood (at Weeks 12, 16, 20, 24, 36, and 48 only).
- Circulating AFP level (at Weeks 12, 24, and 48 only).
- Vector genome PCR in plasma, saliva, urine, stool, and semen (males only) (at Weeks 12, 16, 20, 24, 36, and 48 only).
- PFTs (at Weeks 24 and 48 only).
- 6MWT (at Weeks 24 and 48 only).

- Neurocognitive abilities tests by WASI-II, WPPSI-IV, or BSID-III, and by VABS-II (at Weeks 24 and 48 only).
- MRI of liver (at Weeks 24 and 48 only).
- MRI of brain and cervical spine (at Week 48 only).
- ACTH stimulation (cosyntropin) test (at Week 20 only or at end of prednisone or equivalent corticosteroid taper; see Appendix 3).
- Liver biopsy (at Weeks 24 and 48 only).
- Lumbar puncture (at Weeks 24 and 48 only).

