9.20 Vector Genome PCR

Plasma, saliva, urine, stool, and semen (males only) samples will be analyzed by PCR to determine clearance of SB-913 vector genomes. Each type of sample (plasma, saliva, urine, stool, semen) should be collected until 3 consecutive specimens of that sample type are reported as negative or undetectable for vector genome. Collection of semen samples may be waived for pediatric subjects (cohorts 5 through 8) at the discretion of the Principal Investigator. For details, refer to the Laboratory Manual.

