# 2.2.2 Secondary Endpoints

The following are secondary endpoints for this study:

- Change from Baseline in:
  - o IDS activity measured in blood.
  - o Total GAG, DS GAG, and HS GAG levels (expressed as ratio to creatinine) measured in urine.
- Monthly and annualized frequency and dose of idursulfase (or equivalent ERT).
- AAV2/6 clearance measured by vector genomes in plasma, saliva, urine, stool, and semen by PCR.

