# 4.5 Handling of Dropouts or Missing Data

If laboratory result is below detection limit, it will be imputed to half of detection limit in table and figure. The result will be listed as is in listings.

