#### 4.7 Data Derivations and Transformations

No data derivations or transformations will be performed.

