#### 6.2 Secondary Endpoints and Analyses

Secondary endpoints will be summarized by presenting descriptive statistics of actual values and changes from baseline at each visit, where applicable. The secondary endpoints consist of the changes from baseline over time in the following assessments:

- IDS activity measured in plasma
- Assessments will be conducted at Screening, Baseline, Weeks 2, 4, 6, 8, 12, 16, 20, 24, 36, 48, Months 15, 18, 21, 24, 27, 30, 33, 36/End of Study (EOS), and at any Early Termination Visit. Total GAG, dermatan sulfate (DS) GAG, and heparin sulfate (HS) GAG levels measured in urine

At each sampling time point, the actual value and the change from baseline for IDS activity and urine GAG levels will be summarized using descriptive statistics and plotted over time by treatment cohort.

For subjects who undergo ERT withdrawal, changes from pre- to post- ERT withdrawal in the frequency and dose of ERT infusions will be evaluated and summarized using monthly, quarterly, and annualized total dose and number of infusions. Duration of ERT withdrawal may also be analyzed. The ERT withdrawal period is defined as the date recorded on the ERT Withdrawal Trigger CRF form to the first date after ERT withdrawal recorded on the ERT administration.

• AAV2/6 clearance measured by vector genomes in plasma, saliva, urine, stool, and semen by PCR

AAV2/6 clearance measured by vector genomes in the different samples will be plotted over time by treatment cohort.

CONFIDENTIAL Page 15 of 28

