- c. Serum pregnancy test will be performed at Screening and Baseline visits. Urine pregnancy test will be performed on the Day 0 visit if >7 days from Baseline pregnancy test. Urine pregnancy tests will be performed until Week 48 or until 3 consecutive plasma samples are negative for AAV2/6, whichever occurs first.
- d. Liver panel does not need to be drawn as a separate sample if samples for Clinical Laboratory Tests are obtained at the same visit.
- e. Liver panel will be performed twice a week for the first 20 weeks post-SB-913 infusion, and may be conducted at home if the subject is remote. Blood samples will be drawn 2-4 days apart when possible, except for the first week when it will be drawn on the Day 1 and Day 7 visits. Liver function tests will subsequently be conducted at all indicated study visits.
- f. For adult subjects (cohorts 1 through 4), the assay will be performed on blood or saliva samples; for pediatric subjects (cohorts 5 through 8), saliva samples are preferred.
- g. During Screening, samples for GAG testing in urine will be collected on 3 separate days, each collection occurring at least 7 days after the previous. All samples for GAG testing in the urine must be collected at least 7 days after ERT administration [+/-1 day] but prior to the next ERT infusion.
- h. For IDS/GAG testing in blood, samples must be obtained 7 days after ERT administration (+/- 1 day) and prior to the next ERT infusion. GAG and IDS levels in blood will both be measured concurrently from the same blood sample.
- i. Each type of sample (plasma, saliva, urine, stool, semen) will be collected until 3 consecutive specimens of that sample type are reported as negative or undetectable for vector genome. Collection of semen samples may be waived for male pediatric subjects (cohorts 5 through 8) at the discretion of Principal Investigator.
- j. As permitted by subject's capacity. Neurocognitive abilities testing in pediatric subjects will be done by VABS-II and by WASI-II, WPPSI-IV, or BSID-III, as appropriate based on the Neurocognitive Abilities Assessment performed at Screening.
- k. Baseline MRI of brain and cervical spine may be obtained at the Screening visit (together with MRI for liver) instead of at the Baseline visit at Principal Investigator's discretion.

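### Vector sampling stops per sample type after three consecutive negatives, so by-visit displays of sampled subjects can overstate persistence, and AAV2/6 clearance itself is never estimated

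*SAP*

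**What the plan says.** SAP 2.2.2 lists the secondary endpoint as "AAV2/6 clearance measured by vector genomes in plasma, saliva, urine, stool, and semen by PCR". Protocol 9.20 sets the collection rule: each sample type "should be collected until 3 consecutive specimens of that sample type are reported as negative or undetectable for vector genome". Footnote i of SAP Appendix A carries the same rule.

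For the analysis, SAP 6.2 opens with a general sentence: "Secondary endpoints will be summarized by presenting descriptive statistics of actual values and changes from baseline at each visit, where applicable". Its only text specific to clearance is: "AAV2/6 clearance measured by vector genomes in the different samples will be plotted over time by treatment cohort". Protocol 13.5 plans the same plot.

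Two further provisions matter. SAP 4.7 states: "No data derivations or transformations will be performed". SAP 4.5 gives one data-handling rule: "If laboratory result is below detection limit, it will be imputed to half of detection limit in table and figure". That rule applies to results that were obtained, not to specimens that were never collected.

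Neither document gives, for analysis purposes, a definition of clearance, a proportion cleared, a time to clearance or a censoring rule.

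**The concern.** Whether a late specimen exists depends on the outcome being measured. For a given sample type, a subject with three consecutive negatives stops contributing, and a subject who is still positive goes on contributing. A by-visit summary of the specimens in hand is therefore conditional on not yet having met the stop rule, and its denominator shrinks selectively. With 2 subjects per cohort, or about 4 after expansion, one departure can change the display a good deal.

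Separately, the endpoint is clearance, but the plan displays vector genome levels. A reader of the planned outputs would not find how many subjects cleared, or when. The protocol already works with a criterion of three consecutive negatives, and the analysis does not use it.

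**Working it through.** The documents state no clearance figure, so there is none to reproduce.

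**Inputs from the documents**
- Post-dose visits for all five sample types: Day 7 and Weeks 2, 4, 8 (protocol 6.6, 6.7), then Weeks 12, 16, 20, 24, 36, 48 (protocol 6.8). Plasma has one extra sample on Day 1 (protocol 6.5).
- Stop rule: three consecutive negatives, per sample type.
- Cohort size: 2, or about 4 if expanded (protocol 13.1, SAP 9).

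**Assumptions**
- First-negative times are assumed, because the documents give none.
- There is no return to positive, no visit is missed, results are known before the next visit, and only post-dose specimens count.

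**Step 1: limits set by the schedule.** The earliest stop is Week 4 for saliva, urine, stool and semen (Day 7, Weeks 2 and 4 negative) and Week 2 for plasma (Day 1, Day 7, Week 2). The last scheduled sample is Week 48, so the latest first negative that can be confirmed is Week 24 (Weeks 24, 36, 48).

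**Step 2: a cohort of 4.** Assume first negatives at Weeks 2, 4, 8 and never. The first three subjects give their third negative at Weeks 8, 12 and 16 and are not sampled afterwards.

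| Week | Sampled | Positive | Positive / sampled | Positive / cohort |
|---|---|---|---|---|
| 8 | 4 | 1 | 25% | 1/4 = 25% |
| 12 | 3 | 1 | 33% | 1/4 = 25% |
| 16 | 2 | 1 | 50% | 1/4 = 25% |
| 20 to 48 | 1 | 1 | 100% | 1/4 = 25% |

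Nothing changes in the cohort after Week 8. The whole rise comes from the denominator. In a cohort of 2 with first negatives at Week 2 and never, the display goes from 1/2 = 50% at Week 8 to 1/1 = 100% at Week 12, while the cohort share stays 50%.

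**Step 3: range over assumed clearance times.** Let the time to first negative be exponential with median m weeks, so the cohort share still positive at week t is 2^(−t/m).
- At Week 24, a subject is still sampled unless Weeks 12, 16 and 20 were all negative, that is, unless first negative by Week 12. Share sampled = 2^(−12/m). Positive among sampled = 2^(−24/m) / 2^(−12/m) = 2^(−12/m).
- At Week 48, the three preceding visits are Weeks 20, 24 and 36. Share sampled = 2^(−20/m). Positive among sampled = 2^(−48/m) / 2^(−20/m) = 2^(−28/m).

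| Assumed median m | Week 24: sampled vs all dosed | Week 48: sampled vs all dosed |
|---|---|---|
| 4 weeks | 12.5% vs 1.6% | 0.8% vs 0.02% |
| 8 weeks | 35.4% vs 12.5% | 8.8% vs 1.6% |
| 16 weeks | 59.5% vs 35.4% | 29.7% vs 12.5% |
| 24 weeks | 70.7% vs 50.0% | 44.5% vs 25.0% |

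**Step 4: need for censoring.** The share whose first negative comes too late to be confirmed by Week 48 is 2^(−24/m): 1.6%, 12.5%, 35.4% and 50.0% for the four medians.

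**The case against.** The strongest reply is that this is a small descriptive study and the SAP does not commit to a misleading display. A plot by cohort could be individual lines grouped by cohort, which is natural with 2 subjects. The by-visit sentence is qualified by applicability. SAP 4 reports the number of non-missing observations, so a shrinking denominator would be visible in any table. Subject data are listed (SAP 4, 4.3), so clearance can be read off by hand. SAP 4.7 is also not strictly literal, since SAP 4.3 and 4.4 themselves derive baseline and study day.

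Much of this stands, and it limits the point. It does not remove it. SAP 7.3 says explicitly that liver panel figures are per subject, and SAP 6.2 says no such thing for vector genomes. Listings preserve the information, but they leave the definition of clearance to be chosen after the data are seen. No clearance variable appears anywhere in the SAP.

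A reader might infer four stronger things that the documents do not support:
- **That the displays must plateau or rise.** This needs differing clearance times within a cohort and a remaining signal that does not fall enough to offset departures. In every row of the Step 3 table, positivity among sampled subjects falls from Week 24 to Week 48.
- **That cohort means will be inflated 2-fold or 4-fold.** Those are upper bounds, n divided by the number still sampled (2/1 and 4/1). They need raw arithmetic means and a remaining titre that dominates, and the SAP does not say that the plot shows means.
- **That late visits contain only subjects still shedding.** Each subject contributes up to three negatives, shown at half the detection limit, before leaving. The stop is also per sample type, not per subject.
- **That release from barrier contraception is affected.** Under protocol 4.1 and 9.11 it rests on a subject's own consecutive negative samples. No cohort summary enters it.

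**Conclusion.** The point holds as a weakness in a descriptive secondary analysis that should be corrected. No error rate is involved.

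The direction is structural. If cleared subjects stay negative, the stop rule removes only negatives from the denominator, so positivity among sampled subjects is never below the cohort share. It is above it whenever at least one subject has stopped and at least one is still positive. The size is illustrative: a 25% cohort share displayed as up to 100% in the worked cohort of 4, and gaps of about 11 to 24 percentage points at Week 24 across assumed medians of 4 to 24 weeks (12.5 − 1.6 = 10.9; 59.5 − 35.4 = 24.1). All of this rests on the assumptions listed in the working. It applies to summaries of sampled subjects; individual lines would largely avoid it.

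The absence of any clearance estimate needs no assumption. It follows from SAP 6.2 and 4.7 as written.

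**What to change.** Amend SAP 6.2, with a matching exception in SAP 4.7:

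1. For each subject and sample type, derive time to clearance as the date of the first of three consecutive negative **post-dose** specimens, censored at the last sample if this is not reached. The post-dose condition must be stated, because a Baseline specimen is also collected (protocol 6.3) and could otherwise date clearance before the infusion. Note that a first negative after Week 24 cannot be confirmed by Week 48 on scheduled visits.
2. Report the number and percentage cleared by each visit. The denominator is all dosed subjects in the cohort who provide that sample type, since semen is collected from males only and may be waived in pediatric cohorts.
3. List individual clearance times. A Kaplan-Meier display is optional and, at these cohort sizes, worth doing only pooled across cohorts.
4. Plot individual-subject lines by cohort and mark confirmed clearance. Show any later points as not sampled and presumed negative, not as measured values.

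The cost is a little programming: one derived variable and one table per sample type. No new data and no change to sampling are needed. The price in assumptions is that subjects with confirmed clearance do not return to positive, and the SAP should say so.

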#### **6.3** Exploratory Endpoints and Analyses

Exploratory endpoints will be summarized by presenting descriptive statistics of actual values and changes from baseline at each visit. A by-subject listing will also be provided. The exploratory endpoints consist of the changes from baseline over time in the following assessments:

 Percentage and durability of gene modification at the albumin locus in liver tissue obtained at biopsy

Assessments will be conducted at Baseline, Week 24, and Week 48

FVC measured by PFTs

Assessments will be conducted at Screening, Baseline, Week 24, Week 48, Months 18, 24, 30, 36/EOS, and at any Early Termination Visit.

• Distance walked measured by 6MWT

Assessments will be conducted at Baseline, Week 24, Week 48, Months 18, 24, 30, 36/EOS, and at any Early Termination Visit.

• Joint ROM (ankle, knee, hip, and shoulder)

Assessments will be conducted at Baseline, Week 24, Week 48, Months 18, 24, 30, 36/EOS, and at any Early Termination Visit.

• MRI of liver to evaluate liver and spleen volume

Assessments will be conducted at Screening, Week 24, Week 48, Months 18, 24, 30, 36/EOS, and at any Early Termination Visit.

- MRI of brain and cervical spine to evaluate clinical soft tissue and/or bone
  - Assessments will be conducted at Baseline, Week 48, Month 24, Month 36/EOS, and at any Early Termination Visit.
- Neurocognitive abilities by WASI-II, WPPSI-IV, or BSID-III, and by VABS-II Assessments will be conducted at Baseline, Week 24, Week 48, Months 18, 24, 30, 36/EOS, and at any Early Termination Visit.
- Histopathological exam of liver tissue
- Immune response to AAV2/6, ZFNs, and IDS measured in plasma
  Assessments will be conducted at Screening, Baseline, Weeks 2, 4, 6, 8, 12, 16, 24, 36, 48,
  Months 15, 18, 21, 24, 27, 30, 33, 36/EOS, and at any Early Termination Visit.

AAV-related research biomarkers will also be assessed at baseline.

CTI will be analyzing the change from baseline in Plasma IDS Activity, CSF Pressure, Biomarkers, and MRI of Brain and Neck. All other exploratory analyses will be performed by a third party at Sangamo's discretion.

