9.5 Vital Signs

Vital signs, including height, weight, systolic/diastolic blood pressure, heart rate, respiratory rate, and temperature will be recorded. For details, refer to the Study Reference Manual.

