#### 2.2.3 Exploratory Endpoints

Change from baseline over time in the following assessments:

- Percentage and durability of gene modification at the albumin locus in liver tissue obtained at biopsy.
- Forced vital capacity (FVC) measured by pulmonary function tests (PFTs).
- Distance walked measured by six-minute walk test (6MWT).
- Joint range of motion (JROM).
- MRI of liver to evaluate liver and spleen volume.
- MRI of brain and cervical spine to evaluate clinical soft tissue and/or bone.
- Neurocognitive abilities by WASI-II (Wechsler Abbreviated Scale of Intelligence, Second Edition; Shapiro et al. 2015), WPPSI-IV (Wechsler Preschool and Primary Scale of Intelligence), or BSID-III (Bayley Scales of Infant Development), and by VABS-II (Vineland Adaptive Behavior Scales).
- Histopathological exam of liver tissue.
- Immune response to AAV 2/6, ZFNs, and IDS measured in serum.

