#### 3. INVESTIGATIONAL PLAN

#### 3.1 Study Design

This is a Phase 1/2, multicenter, open-label, single-dose, dose-ranging study with sequentially enrolled age cohorts: age  $\geq$ 18 (adult cohorts 1 through 4), age 12-17 (pediatric cohorts 5 and 6), and age 5-11 (pediatric cohorts 7 and 8).

Subjects who satisfy all eligibility criteria will be enrolled into one of the following treatment

CONFIDENTIAL Page 9 of 28

cohorts:

Cohort #	Age Range (years)	Total Dose (vg/kg)	# Subjects
1	≥18	5.00E+12	2
2	≥18	1.00E+13	2
3	≥18	5.00E+13	2
4	≥18	1.20E+14	2
5	12-17	5.00E+13	2
6	12-17	TBD	2
7	5-11	TBD	2
8	5-11	TBD	2

Two subjects will be enrolled in each cohort, and will be dosed at least 4 weeks apart. SMC (Safety Monitoring Committee) review occurs after at least 4 weeks of safety data is available from 2 subjects in each cohort. The pediatric cohorts will be enrolled only after review of cumulative adult safety data by the SMC. The starting dose for pediatric cohorts 6 through 8 will be decided based on SMC review of study data, and must meet pre-defined safety criteria. Approximately 2 additional subjects may be added to any age cohort after SMC review of study data if safety criteria are met, with up to a total of 32 subjects in the study.

For subject inclusion and exclusion criteria, please refer to study protocol SB-913-1602. Subjects that do not complete at least 12 months of the study may be replaced with other subjects. The duration of the study participation will be approximately 39 months for each subject, divided into approximately 3 months for Screening followed by 36 months for treatment and study follow-up. Upon completion of the study, subjects will be asked to participate in a separate Long-term Follow-up Study to monitor the long-term safety of SB-913.

A detailed schedule of events for the study can be found in Appendix A.

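### For Cohorts 5-8 (ages 5-17), the SAP summarises organ volume, 6MWT distance and FVC as raw change over up to 36 months with no size- or age-adjusted version, so growth is confounded with treatment.

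*SAP*

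**What the plan says.** - **Method.** SAP 6.3: "Exploratory endpoints will be summarized by presenting descriptive statistics of actual values and changes from baseline at each visit". The list under it includes "MRI of liver to evaluate liver and spleen volume" and "Distance walked measured by 6MWT", and FVC, which SAP 2.2.3 defines only as "Forced vital capacity (FVC) measured by pulmonary function tests (PFTs"). No FVC unit is given. SAP 6 also allows year-on-year change for selected parameters, again without adjustment.
- **Derivations.** SAP 4.7: "No data derivations or transformations will be performed".
- **Population and duration.** SAP 3.1 defines "age 12-17 (pediatric cohorts 5 and 6), and age 5-11 (pediatric cohorts 7 and 8"), and participation of "approximately 3 months for Screening followed by 36 months for treatment and study follow-up". SAP 3.2.1 confirms an open-label study without randomisation. All cohorts receive SB-913.
- **Protocol.** Section 13.6 lists the same unadjusted variables and leaves analysis details to the SAP.
- **Body size.** Protocol 9.5: "Vital signs, including height, weight, systolic/diastolic blood pressure, heart rate, respiratory rate, and temperature will be recorded". SAP 7.4 summarises height and weight in their own right but does not link them to FVC, organ volume or walking distance.

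Neither document mentions percent-predicted values, volume per kg, multiples of normal, z-scores or age and height references for these three measures.

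**The concern.** A child followed for up to three years grows. Lung volume, liver and spleen volume and walking distance all tend to increase with body size. With no untreated children for comparison, a raw change from baseline adds growth to any treatment effect, and the two cannot be separated.

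The direction differs by endpoint. For liver and spleen volume, where benefit would be a reduction, growth works against the effect and can hide it. For 6MWT distance, and for FVC in litres, benefit would be an increase, so growth can look like benefit.

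Protocol 1.1 names pulmonary function, hepatosplenomegaly and exercise capacity as the areas in which enzyme replacement has shown improvement. Readers will therefore look to these three measures for signs of activity in the paediatric cohorts.

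**Working it through.** **Stated figure.** The plan has no power calculation (SAP 9). Its one figure, a maximum of 32 subjects, is reproduced: 8 cohorts × 2 = 16 planned, and 8 × (2 + 2) = 32. The paediatric share is 4 × 2 = 8, up to 4 × 4 = 16.

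**Inputs from the documents.** Ages 5-17 in Cohorts 5-8 and follow-up to 36 months (SAP 3.1); weight of at least 20 kg at Screening (Protocol 4.2); possible transfer to long-term follow-up after 12 months (Protocol 3.4).

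**Assumptions, not from the documents.** Starting height h is 110-165 cm, growing g = 1-6 cm/year. Starting weight w is 20-60 kg, gaining m = 1-4 kg/year. FVC in litres scales with height to the power k = 2 to 3, organ volume with weight, and 6MWT distance with height. There is no treatment effect.

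**Drift from growth alone at 36 months**

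| Measure | Formula | Low end | High end |
|---|---|---|---|
| FVC in litres | ((h + 3g)/h)^k − 1 | (168/165)² − 1 = +3.7% | (128/110)³ − 1 = +57.6% |
| Liver or spleen volume | (w + 3m)/w − 1 | 63/60 − 1 = +5.0% | 32/20 − 1 = +60.0% |
| 6MWT distance | 3g/h | 3/165 = +1.8% | 18/110 = +16.4% |

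Mid-range cases: FVC from 130 cm at 3 cm/year with k = 2.5 gives (139/130)^2.5 − 1 = +18.2%. Organ volume from 30 kg at 2 kg/year gives 36/30 − 1 = +20%.

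**Drift at 12 months** (same formulas, one year of growth)

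- FVC in litres: (166/165)² − 1 = +1.2% to (116/110)³ − 1 = +17.3%.
- Organ volume: 61/60 − 1 = +1.7% to 24/20 − 1 = +20%.
- 6MWT: 1/165 = +0.6% to 6/110 = +5.5%.

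**Masking of a real effect.** Suppose volume per kg truly falls by 20% over 36 months. The raw change is 0.8 × (w + 3m)/w − 1.

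- 20 kg gaining 2 kg/year: 0.8 × 26/20 − 1 = +4%.
- Across the assumed range: 0.8 × 63/60 − 1 = −16% to 0.8 × 32/20 − 1 = +28%.

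In the first case, a true per-kg fall of 1 − 20/26 = 23.1% would show as exactly no change.

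Under these assumptions, a correctly size-scaled measure shows 0% drift, by construction.

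**The case against.** **SAP 4.7 is not applied literally.** SAP 4.3 derives a mean pre-dose baseline for GAG and IDS, SAP 4.5 imputes half the detection limit, and SAP 2.2.2 expresses urine GAG as a ratio to creatinine. A reader might infer that the SAP deliberately forbids normalisation. The documents do not show such intent. They do show that no adjustment is specified and that one sentence, taken at face value, excludes it.

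**The FVC unit is unknown.** If the case report form captures percent-predicted FVC, that is already the observed value and growth is largely accounted for. Details of the tests sit in the Study Reference Manual and Imaging Guidelines, which are not available here. It would be too strong to say that FVC will show false benefit; this depends on the unit.

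**The drift may be small in some children.** Older adolescents may grow little, and 36 months is a maximum. Protocol 8.2 lists interference with growth among glucocorticoid effects. These points stand and explain the wide ranges. It would also be wrong to carry the volume figures over to 6MWT, where the drift is much smaller.

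**Adults and children are kept apart, and data are listed.** Cohorts do not mix adults and children, and SAP 6.3 provides by-subject listings. A reader might infer that the raw scale spoils an adult-paediatric comparison, particularly as Cohorts 3 and 5 share a dose. No such comparison of these endpoints is planned, so that claim is not made. Listings let a careful reader look at growth, but they do not remove it from the planned change-from-baseline tables.

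**Another party may run the analyses.** SAP 6.3 gives these endpoints to a third party at the sponsor's discretion, although SAP 4 assigns all exploratory analyses to the contract research organisation. Neither section supplies a different method.

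**Conclusion.** The point holds as a gap in the paediatric part of the exploratory analysis. As written, raw change in liver and spleen volume and 6MWT distance in Cohorts 5-8 mixes growth with treatment. The same is true of FVC if it is recorded in litres.

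The direction is clear in any child who grows, but the size is illustrative. It rests on the assumed growth rates and scaling above, so it bounds the problem and does not predict it. On those assumptions the 36-month drift can be as large as an effect of interest for organ volume and FVC in litres. For 6MWT it is modest.

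The endpoints are exploratory and descriptive, and paediatric enrolment depends on Safety Monitoring Committee review. The primary safety objective, the sample size and adult Cohorts 1-4 are untouched. This is a cheap improvement worth making, not a flaw in the study's main purpose.

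**What to change.** In SAP 6.3, for Cohorts 5-8:

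1. State the unit in which FVC is recorded, and present percent-predicted FVC.
2. Present liver and spleen volume scaled to body size, per kg and also with a height-based scaling. Protocol 8.2 lists weight gain and fluid retention with glucocorticoids, and the planned taper lasts about 20 weeks. At Week 24, the first post-dose liver MRI, a per-kg value could therefore fall because weight rose.
3. Present height-adjusted or percent-predicted 6MWT distance.
4. Keep the raw values next to each adjusted version, and name the reference equations in advance.
5. State that this applies to whichever party runs the analyses, and reconcile SAP 4 with SAP 6.3 on who that is.

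Amend SAP 4.7 to permit these derivations.

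No new assessments are needed. Vital signs, which include height and weight, are scheduled at every visit that SAP 6.3 lists for these three measures. The cost is a few derived variables. The drawback is that reference equations fit MPS II stature imperfectly, which is why the raw values stay alongside.
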